6.1.2.6.1 RECOMMENDATIONS FOR USE OF OPTUNE

All patients treated with Optune will be required to shave their heads to initiate array placement and Optune therapy. Array placement will be performed based on the transducer array map calculated during treatment planning. It is recommended that treatment with the device be continuous with breaks allowed for personal needs (e.g., showering, array exchange). Breaks should be no more than 1 hour twice daily.

Use compliance is aimed at a minimum of 50% (12 hours) with the goal of achieving at least 75% (18 hours) of the time per day on average. In addition, investigators may grant brief breaks in device treatment that last no more than 3 days in any 30-day period at the investigator's discretion. Subjects should be counseled by study staff if compliance reports show less than 50% compliance.

Optune is programmed by Novocure to deliver 200 kHz TFields in two sequential, perpendicular field directions at a maximal intensity of 707 mARMS. There will be no adjustments made to the device by investigators or patients/caregivers.

It is recommended that patients replace the transducer arrays 2-3 times per week with the help of a caregiver. At each array replacement, it is recommended that the patient's scalp be re-shaved and skin treated according to the guidelines in section "Skin Care Guidelines."

There will be no dose adjustments to the device for adverse events. Reasons for breaks in treatment for longer than 24 hours will be documented.

Optune therapy will be stopped in the following cases:

- The occurrence of serious adverse events probably or definitely related to treatment with TFields
- Clinical and functional deterioration considered by the investigator to be prohibitive of continuing treatment.
- After 24 months or after second progression, whichever occurs first.

Treatment with the Optune does not need to be terminated in the following situations:

- Toxicity due to temozolomide treatment
- Radiological progression alone will not lead to termination of TFields treatment, but to replacement of the temozolomide treatment with best standard of care second line therapy:
 - Re-operation
 - Local radiation therapy
 - Second line therapy

6.1.2.6.2 SKIN CARE GUIDELINES

If the skin beneath the transducer arrays is inflamed, it is recommended that a prescription strength steroid ointment (e.g. 3% hydrocortisone or 0.05-0.1% Clobetasol) be prescribed to the patient. The patient or caregiver should apply the ointment after removing the arrays and cleaning the scalp with baby oil and gentle soap. The ointment should be left on the scalp for at least 30 minutes prior to washing the skin with a mild shampoo and applying a new set of arrays.

At each array replacement, it is recommended that the new set of arrays be shifted by approximately 2 cm compared to the previous layout so that the array discs are placed between the areas of skin irritation. At the next array replacement, the arrays should be shifted back to their original location.

If the dermis is breached (ulcers, open sores, punctate lesions, cuts, etc.), it is recommended that an antibiotic ointment (e.g. bactroban) be prescribed and used in place of the steroid ointment.

6.2 Preparation/Handling/Storage/Accountability

6.2.1 Acquisition and accountability

Temozolomide is a standard of care therapy widely available throughout the U.S. Each site will utilize their hospital/local pharmacies for this study.

Optune devices will be delivered to patients and maintained by the Novocure network of Device Site Specialists across the U.S. Subjects will be met at their house and trained on device use. Device supplies will be delivered directly to the subject. The DSS will revisit as required for usage/compliance reporting, device maintenance, resupply, and to answer any questions the patient has about the device.

6.2.2 Formulation, Appearance, Packaging, and Labeling

The complete package insert for temozolomide will accompany this protocol in lieu of an Investigator's Brochure.

The complete Optune Instructions for Use and Device Manual will accompany this protocol in lieu of a Device Manual.

Additionally, the Optune DSS may provide the patient with Optune Patient Information and Operation Manual, Optune Travel Support Brochure, Optune Patient Scalp Care Guidelines, etc. These are educational resources published by Novocure to better assist patients in understanding and using the device.

6.2.3 Product Storage and Stability

6.2.3.1 Temozolomide

Storage

- Store (temozolomide) Capsules at 25°C (77°F); excursions permitted to 15-30°C (59-86°F)
- Store (temozolomide) for Injection refrigerated at 2-8°C (36-46°F).
 - After reconstitution, store reconstituted product at room temperature (25°C [77°F]). Reconstituted product must be used within 14 hours, including infusion time.

The above storage guidelines are taken from the package insert; please see full insert for full details.

6.2.3.2 Optune

6.2.3.2.1 STORAGE CONDITIONS

- Temperature range: 23°F to 104°F for the device and additional parts
- Temperature range: 41°F to 81°F for the transducer arrays

- Relative humidity range: 15-75% for the device and additional parts
- Relative humidity range: 35-50% for the transducer arrays

6.2.3.2.2 TRANSPORT CONDITIONS

Transportation of the device and additional parts is possible using air/ground transportation in weather protected conditions as specified below:

- Temperature range: -13°F to 104°F
- Maximal relative humidity 15-75%
- No direct exposure to water

Transportation of the transducer arrays is possible using air/ground transportation in weather protected conditions as specified below:

- Temperature range: 32°F to 104°F
- Maximal relative humidity 15-75%
- No direct exposure to water

Please see the Optune Instructions for Use and Device Manual for full details.

6.2.4 Preparation

No preparation of either temozolomide or the Optune device is required by study staff. Temozolomide is administered per package insert. Optune is delivered, set-up, trained, and maintained by the Novocure DSS in the site's local area per clinical standard of care.

6.3 Correlative Studies

6.3.1 Tumor Tissue Specimens

6.3.1.1 Collection of specimens

Formalin fixed and paraffin embedded (FFPE) samples will be obtained from pathology or research tissue banks from primary tumors and first recurrent tumors, when available. One FFPE tissue block or fifteen slides of 20 µm thick section will be required for analysis. At least 20 pairs of primary tumors and first recurrent tumors from patients treated only with RT and concurrent temozolomide followed by adjuvant temozolomide, and not with TTFields or any other modalities (drug, radiation or device), are needed.

The Coordinating Center will obtain at least 20 historical paired samples from patients with the same tumor type or GBM before and after being treated with temozolomide and RT, but not with TTFields, over the last 5 years at the same participating institutions.

Sequencing analyses will be obtained by standard of care sequencing (immunohistochemistry or next-generation sequencing), from which mutation burden data will be obtained. Mutation burden will be expressed as number of mutations per Mb and will be extracted from sequencing reports for primary tumors and first recurrent tumors, where available.

6.3.1.2 Handling of specimens

FFPE samples, or pathology slides, will be used for standard H&E and immunohistochemical (IHC) staining for biomarkers for TILs and immunogenic cell death to be performed at the University of Florida.

IHC will be performed for the following, but not limited to, biomarkers: CD4, CD8, CD19, and CD45 (immune cells), AIM2, ACS and cGAS (immunogenic cell death), ISG15, INFalpha, and INFbeta (type 1 interferon response). Results will be expressed as percentage of cells with positive staining for each marker.

6.3.2 Electric Field Modeling

Tumor Treating Fields are alternating electric fields at 200 kHz that can penetrate from the surface of the scalp into the brain to exert their anti-mitosis effect on dividing tumor cells. They have to first pass through the calvarium and subarachnoid space where they are attenuated by resistive property of bone and the conductive property of the cerebrospinal fluid. The remaining fields then reach the gray and white matters where they are either augmented or attenuated, depending on the local tissue properties and the geometry of structures such as the frontal, temporal and posterior horns of the lateral ventricles. As a result of these interferences, the amount of electric fields that reaches the gross tumor volume cannot be calculated precisely but can only be approximated numerically by methods such as finite element analysis [62].

6.3.2.1 Secondary imaging analyses

In addition, secondary analyses will be performed to determine the extent of correlation with respect to patient age, Karnofsky Performance Status, dexamethasone dosage, other non-therapeutic supportive medications and the number of cycles of chemotherapy, targeted therapy, biological agents or immune therapies received.

Additional analyses will be conducted to also determine the correlation with fluctuations in laboratory values in complete blood counts, differential, electrolytes, liver function tests, as well as histological and genetic

parameters, such as Ki67, presence or absence of IDH-1 mutation, MGMT methylation status and/or somatic mutations found in next generation sequencing.

6.3.2.2 MRI Acquisition and DICOM images

The process of numerical estimation of electric field strength at the gross tumor volume consists of a number of steps. First, gadolinium-enhanced MP RAGE sequences will be acquired using MRI in one axis and reconstructed in the other two axes resulting in axial, coronal and sagittal images. Standard T2, FLAIR and pre-gadolinium sequences will also be obtained per local care standards. The field of view of the images should include the surface of the scalp (Fig. 7). These images will be exported as DICOM images.

Second, the DICOM images will be imported into a tissue segmentation software program as previously described [69]. Third, both intracranial and extracranial structures, including scalp, skull, dura, cerebrospinal fluid, gray matter, white matter and bilateral ventricles, will be segmented and meshed before solving using finite element methods [62].

Lastly, the electric field strength and the specific absorption ratio at the gross tumor volume will be tabulated using various electric field strength parameters, including EAUC, EV150, E95% and E50%, and specific absorption ratio parameters, including SARAUC, VSAR7.5, SAR95% and SAR50%. Together, these parameters will allow the comparison among patients of the electric field strength, as well as the amount of energy deposited, at the tumor.

The electric field and specific absorption ratio parameters will be correlated with measures of clinical outcome, including response rate, progression free survival and overall survival. Spearman rank-order correlation will be performed between the non-parametric electrical and clinical outcome variables.

The DICOM images will be obtained for analysis at baseline, each two months per protocol, and at the time of first and second progression. These analyses will be performed at Beth Israel Deaconess Medical Center. Analysis will be completed within two years of the last patient's enrollment.

[figure not shown]

Figure 7. MRI image samples demonstrating field of view of the images must include the surface of the scalp. Incorrect image on the left does not include full scalp surface where indicated by arrows. The correct image at the right does include the surface of the scalp around the entire head.

6.4 Study Intervention Compliance

Temozolomide compliance will be measured by subject self-report.

Optune compliance will be measured on each device and a monthly report provided to the subject and Site Investigator by the DSS.

Optune compliance will be addressed according to the following table:

TABLE 9: OPTUNE COMPLIANCE REQUIREMENTS

Subject Compliance in previous 4-week period per device report	DSS	Study Staff
≥ 75%	n/a	Reinforce good compliance report
74% to 50%	
 ○ Re-train patient on device compliance requirements ○ barriers to compliance will be addressed 	n/a
≤ 49%	
 ○ Re-train patient on device compliance requirements ○ barriers to compliance will be addressed 	Counsel subject during study visit re: need for additional use of device and identify any remaining barriers

6.5 Concomitant Therapy

For this protocol, a prescription medication is defined as a medication that can be prescribed only by a properly authorized/licensed clinician. Medications to be reported in the Case Report Form (CRF) are concomitant prescription medications, over-the-counter medications and supplements.

Medication History should include the Chemoradiation treatment window, or at least 90 days of Medication History, whichever is greater.

7 STUDY INTERVENTION DISCONTINUATION AND PARTICIPANT DISCONTINUATION/WITHDRAWAL

7.1 Discontinuation of Study Intervention

Discontinuation from study treatment does not mean discontinuation from the study, and remaining study procedures should be completed as indicated by the study protocol. If a clinically significant finding is identified (including, but not limited to changes from baseline) after enrollment, the investigator or qualified designee will determine if any change in participant management is needed.

Any serious adverse event deemed life threatening by the treating physician that is definitely related to the study device will be cause for immediate cessation of treatment for the patient. Patient follow up will continue after such an event.

7.2 Procedures for Orderly Termination of Participation

Participants are free to withdraw from participation in the study at any time upon request.

An investigator may discontinue or withdraw a participant from the study for the following reasons:

- The investigator may remove a patient from the study in case of not complying with study protocol.
- If any clinical adverse event (AE), including a laboratory abnormality, or other medical condition or situation occurs such that continued participation in the study would not be in the best interest of the participant

The reason for participant discontinuation or withdrawal from the study will be recorded on the electronic Case Report Form (eCRF). Subjects who sign the informed consent form and do not receive the study intervention may be replaced. Subjects who sign the informed consent form, and receive the study intervention, and subsequently withdraw, or are withdrawn or discontinued from the study, will not be replaced.

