3 OBJECTIVES AND ENDPOINTS

TABLE 2: OBJECTIVES & ENDPOINTS

OBJECTIVES	ENDPOINTS	JUSTIFICATION FOR ENDPOINTS
Primary		
To determine whether TTFIELDS combined with adjuvant temozolomide increases OS in patients with newly diagnosed Grade II and III astrocytoma with TERT promoter mutation only compared to historical and contemporaneous controls.	OS measured in days from Study Day 0 until death. If the study ends and the participant is still living, OS will be measured in days from Study Day 0.	OS remains the primary concern within this patient population. Intent to Treat analysis will be used to determine if this objective is met.
Secondary		

 To determine whether the combination of TTFIELDS and adjuvant temozolomide is safe in the newly diagnosed high-risk Grade II and III astrocytoma. To determine whether TTFIELDS combined with adjuvant temozolomide increases PFS in patients with newly diagnosed Grade II and III astrocytoma with TERT promoter mutation only compared to historical and contemporaneous controls. To evaluate QOL using KPS, EORTC QLQ-C30/BN20, and MMSE in patients treated with TTFIELDS combined with adjuvant temozolomide compared to 	
 PFS measured in days from Day 0 to progression Safety measured by incidence and severity of Adverse Events and Toxicities. Quality of life measured by KPS, EORTC QLQ-C30/BN20, and MMSE Correlation between % Compliance with TTFIELDS and OS 	Safety, Efficacy, and Quality of Life measures for a more complete view of the effects of the study treatment(s).

historical and contemporaneous controls.		
Tertiary/Exploratory		

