4.4 End of Study Definition

A participant is considered to have completed the study if he or she withdraws consent, is withdrawn by the investigator, is declared lost to follow-up, or dies.

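### Investigator removal under section 7.2 can end survival follow-up in the interventional arm only, and neither the intent-to-treat set nor an OS censoring rule is defined to deal with it

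*Combined protocol and SAP*

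**What the plan says.** Section 7.2 gives the investigator two grounds for taking a participant out of the study. The first is non-compliance: "The investigator may remove a patient from the study in case of not complying with study protocol". No threshold is given. The second is an adverse event, laboratory abnormality or other medical condition that makes continued participation not in the patient's interest.

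Section 4.4 makes such removal an end of participation: "A participant is considered to have completed the study if he or she withdraws consent, is withdrawn by the investigator". Section 11.1.9.2 lists withdrawal among the points at which survival follow-up stops.

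On the primary analysis, Table 2 (section 3) says "Intent to Treat analysis will be used to determine if this objective is met". It defines the endpoint as "OS measured in days from Study Day 0 until death". For patients without a death it covers only one case: "If the study ends and the participant is still living, OS will be measured in days from Study Day 0". Section 10.3 does not define an intent-to-treat set, and it describes the interventional population by treatment received, TTFields included.

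On replacement, section 7.2 says "Subjects who sign the informed consent form and do not receive the study intervention may be replaced". Those who received the intervention "and subsequently withdraw, or are withdrawn or discontinued from the study, will not be replaced".

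Control data, including date of death, come only from chart review (section 9.5).

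**The concern.** Stopping treatment and leaving the study are different events, and section 7.1 says so. Section 7.2 adds a separate power to end study participation, and sections 4.4 and 11.1.9.2 carry that through to survival status. If the patients removed are mainly those getting worse, their deaths drop out of the interventional arm and not out of the control arm. The log-rank comparison would then favour TTFields. The trial is open-label and non-randomised, with OS tested at one-sided 0.05, so a handful of discretionary removals could matter.

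There is a smaller gap at the start of treatment. The OS clock starts at Day 0, the first adjuvant temozolomide dose, while Optune may start up to two weeks later (section 8.1.1). Section 7.2 does not say whether a patient who has taken temozolomide but never started Optune has received the intervention, and so whether that patient may be replaced.

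**Working it through.** **Inputs from sections 10.1 and 10.2.** 90 interventional and 90 control patients; control median OS 22 months; Weibull survival with shape k = 2.0; one-sided log-rank test at 0.05; accrual over 36 months plus 24 months of follow-up, so 24 to 60 months per interventional patient.

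**Assumptions.** Follow-up is uniform on 24 to 60 months in both arms, which reproduces Table 10 well. The documents give no removal rate, timing or reason, so all removal figures below are assumed.

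**Reproducing Table 10 (90+0 controls, k = 2.0, 6-month gain).**
- HR = (22/28)^2 = 0.617, and |ln HR| = 0.482.
- Expected deaths are 78.4 (control) + 67.6 (interventional) = 146.0.
- z = 0.482 × √(146.0 × 0.25) − 1.645 = 0.482 × 6.04 − 1.645 = 1.27, so power is 0.898. The plan states 0.894.

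**Simulation, 10,000 trials per cell.** Survival time is T = median × (E/ln 2)^(1/k), with E unit exponential. Each interventional patient is liable to removal with probability q. A removed patient is censored at time R if R falls before 24 months and before the end of observation. Two rules for R were used:
- unrelated to survival: R uniform on 0 to 24 months;
- tracking decline: R = T minus a uniform lead of 0 to 6 months (or 0 to 12).

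With no removal, the error is 0.051 and power at a 6-month gain is 0.896.

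One-sided error when there is no treatment effect (mean number removed of 90 in brackets):

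| q | Unrelated | 0–6 months before death | 0–12 months before death |
|---|---|---|---|
| 5% | 0.052 (3.5) | 0.075 (2.9) | 0.072 (3.2) |
| 10% | 0.051 (7.0) | 0.107 (5.8) | 0.108 (6.4) |
| 20% | 0.050 (14.1) | 0.214 (11.6) | 0.200 (12.9) |

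The Monte Carlo standard error near 0.05 is √(0.05 × 0.95/10,000) = 0.002. Repeat runs of the 0–6 month rule gave 0.076 for about 3 removed, and 0.110 and 0.118 for about 6.

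Power at a 6-month gain falls to 0.890, 0.883 and 0.869 when removal is unrelated to survival. Under the 0–6 month rule it rises to 0.920, 0.942 and 0.974, which is spurious.

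An intermediate case removes patients who would die before 18 months more often than the others (15% v 5%, or 20% v 10%) but at uniform times over 0 to 24 months. It gives 0.060 to 0.066.

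**Replacement.** The modelled chance of death within two weeks (0.5 months) of Day 0 is 1 − exp(−ln 2 × (0.5/22)^k). This is 0.04% at k = 2.0 and 0.08% at k = 1.8, or 0.03 to 0.07 expected deaths among 90.

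**The case against.** The best defence is that the protocol already handles the likely reasons for removal without taking anyone off study.
- Low Optune use leads to retraining and counselling (sections 6.1.2.6, 6.1.2.6.1 and Table 9).
- Clinical and functional deterioration is listed as a reason to stop Optune, not to leave the study (section 6.1.2.6.1).
- Patients taken off therapy for toxicity or progression are telephoned every 3 months until death (section 6.1.2.6).
- Section 7.1 separates stopping treatment from leaving the study.
- A legally authorised representative is recorded so that survival follow-up can continue (section 5.5).
- Table 2 lists the correlation of device compliance with OS as an endpoint, which presupposes that poor compliers stay in.

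This stands as a reason to expect few removals. It does not close the route, because none of these passages limits the power in section 7.2 or restores follow-up after it is used.

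Three stronger readings are tempting, and the documents do not support them.
- A reader might infer that section 7.2 contradicts the intent-to-treat analysis. No text excludes removed patients from analysis, treated patients who are withdrawn are not replaced, and censoring a patient is not excluding one.
- A reader might infer that any removal inflates the error. Removal at times unrelated to survival leaves it at 0.05. Picking patients at random but censoring each at a fixed fraction of their own survival time is not random removal, because that time is tied to death.
- A reader might infer that replacement hides early deaths. Replacing consenters who never start is ordinary when OS runs from Day 0, and section 6.1.2.4 already makes a missed Cycle 1 window a screen failure. The case of temozolomide started but not Optune is an ambiguity: the synopsis and section 6.1.1.1 describe study treatment as the combination, so such a patient has arguably begun it. Selection on prognosis beyond two-week deaths is possible but cannot be sized from the documents.

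**Conclusion.** The point holds as a gap that should be fixed, not as a demonstrated bias. Taken together, sections 7.2, 4.4 and 11.1.9.2 allow survival follow-up to end at the investigator's decision in the interventional arm alone, and the plan does not say who is in the primary analysis or how such patients are censored.

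The size depends entirely on why and when patients are removed. Unrelated to survival, the cost is a little power. Shortly before death, about 3 removals in 90 take the one-sided error from 0.05 to about 0.076, and about 6 roughly double it to about 0.11. These figures assume the plan's Weibull model with k = 2.0, 90 patients per arm, uniform 24 to 60 months of follow-up, and removal rates that the documents do not supply. The replacement wording is a secondary matter of definition.

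**What to change.** 1. In section 7.2, state that investigator removal, on either ground, ends study treatment only. Align sections 4.4 and 11.1.9.2 so that vital status continues to be collected, by the existing 3-monthly contact, the legally authorised representative or chart review, unless the patient withdraws consent for follow-up.
2. In section 10.3 and Table 2, define the OS analysis set as all interventional patients who start adjuvant temozolomide at Day 0, whether or not Optune was started.
3. In section 7.2, allow replacement only for patients who do not reach Day 0.
4. In Table 2 or section 10.2.1, censor OS at the date last known alive, and add a sensitivity analysis that counts removals as events.

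The cost is minor rewording and a small amount of extra follow-up for removed patients. With survival follow-up kept for everyone, the simulated error is 0.051 and power at a 6-month gain is 0.896, in line with the planned 0.05 and 0.894.
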